Low birth weight is not only a predictor of prenatal morbidity and mortality, but studies have found that it also increases the risk for non-communicable diseases such as diabetes mellitus and cardiovascular diseases in later life (10-11)

The global magnitude of LBW is 15.5 %. In Ethiopia, the prevalence of under-five mortality ranges from 53 to 169 per 1000 live births out of this neonatal mortality which is mainly attributed by LBW accounts the largest portion (12)

In multiple studies, different factors have been identified as determinant for LBW, and among these are young maternal age at pregnancy, birth order, the family's income, maternal under nutrition, maternal underweight, pregnancy related complications, preterm birth, chronic medical illness, multiple pregnancies, history of previous LBW, insufficient prenatal care, and maternal smoking (13 14 15 16).

Statement of problem

Consequences of anemia include increased maternal and perinatal mortality, impaired physical and cognitive development of children and reduced work productivity (9)

Severe anemia (<7 g/L) during pregnancy has been associated with major maternal and fetal complications. It increases the risk of preterm delivery, low birth weight, intrauterine fetal death, neonatal death, maternal mortality, and consequently infant mortality. (17)

Pregnant woman that live in rural areas [18], lack of raw vegetables in their diet [19], illnesses [18] and low levels of education [20] are also major determinants of anemia. Similarly, anemia prevalence decreases as wealth status increases [21.],

Further, studies conducted in Ethiopia have shown that the type of residence, gravidity, interval between pregnancies, and malaria infection during pregnancy have been associate with gestational anemia. (22)

Working to improve the nutritional status of pregnant women through supplementation of vitamin A, iron, and iodine is important to minimize the risk of anemia [23]

The reason of anemia during pregnancy in developing countries includes nutritional deficiencies of iron, folate, and vitamin B12 and parasitic diseases, such as malaria and hookworm. The relative contribution of each of these factors to anemia varies greatly by geographical location, season, and dietary practices [1].

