A matched Case Control study conducted in Malaysia, after multivariable conditional logistic regression analysis identified younger maternal age, previous history of LBW infants, prematurity, and current hypertension as significant factors associated with LBW infants (30).

Registry-based retrospective cohort study conducted in Northern Tanzania showed that preeclampsia, eclampsia, chronic hypertension, maternal anemia, HIV status, smoking during pregnancy, caesarean section delivery, placental abruption, placenta Previa, PROM, maternal underweight, obesity and female gender of baby were significantly associated with delivery of low birth weight infants (31).

A cross-sectional study conducted in Kenya showed that delivery of LBW baby in a previous birth and female infant were independently associated with LBW (32). Another retrospective analysis of cohort study conducted in Kenya also found that increasing parity was associated with reduced odds of LBW (33).

According to a meta-analysis of 895 studies conducted by Kramer, birth weight is governed by two major processes: duration of gestation and intrauterine growth rate. Factors with well-established direct causal impacts on intrauterine growth include infant sex, racial/ethnic origin, maternal height, pre-pregnancy weight, paternal weight and height, maternal birth weight, parity, history of prior LBW infants, gestational weight gain and caloric intake, general morbidity and episodic illness, malaria, cigarette smoking, alcohol consumption, and tobacco chewing. In developing countries, the major determinants of IUGR are Black or Indian racial origin, poor gestational nutrition, low pre-pregnancy weight, short maternal stature, and malaria. For gestational duration, only pre-pregnancy weight, prior history of prematurity or spontaneous abortion and cigarette smoking have well established causal effects (34).

A follow up study conducted in Malawi also found a positive association between maternal HIV infection and LBW. HIV infection was strongly associated with LBW after adjusting for potential confounders. In similar study multivariate analyses of mean birth weight revealed a 138-g reduction in birth weight by HIV infection (35). Another study conducted Malawi also indicated that, HIV positive mother had 1.77 times more likely than

HIV negative mothers to give birth to LBW infant (36). Maternal HIV infection was also associated with 2 times increased chance of LBW in Kenya (37).

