Studies conducted in different parts of Ethiopia showed different factors to be associated with LBW. For instance a case-control study conducted in Bale zone, Ethiopia also showed that maternal age at delivery less than 20 years and residing in rural area were socio-economic variables associated with low birth weight. Maternal risk factors like occurrence of health problems during pregnancy, maternal BMI less than 18 kg/m², maternal height less than 1.5m, inter-pregnancy interval less than 2 years, absence of ANC and history of khat chewing were also associated with low birth weight (38).

An observational cohort study on pregnant women conducted in Kersa, Ethiopia, also showed that LBW is significantly associated with maternal mid upper arm circumference (MUAC) less than 23 cm and not attending ANC (39).

Association between Anemia and LBW

A review of different literature showed that association between anemia and birth weight among pregnant mothers.

According to a facility based case-control study conducted in Ahmadabad city, India, showed there is relationship between use of anemia and LBW. According to this review anemia were found to be significant independent risk factor for LBW (40).

A hospital based retrospective cohort study conducted among infants born to HIV-infected women in public hospitals in Northwest Ethiopia showed maternal anemia was significantly associated with LBW(41).

[figure not shown]

Figure 1 Conceptual framework showing birthweight and associated factors among pregnant women attending ANC clinic in Sidama Region, 2022. Developed from different literatures reviewed

Objective

To establish association between anemia and birth weight among pregnant women attending ANC clinic at public hospitals of Sidama region, Ethiopia, 2022.

Methodology

Study area

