The study will be conducted in public health facilities of Sidama national regional state. It is located about 275 Kilometers away from Addis Ababa. It has 30 Districts, 1 city administration and 6 town administration with a total of 576 kebeles of which 524 of them are rural and 52 are urban. It is one of the highly populated areas in Ethiopia, having a total population of about 4 million people residing on 72100 hectare of land. Out of the total population 5.7% are urban and 94.3% rural residents. Sidama is characterized by three agro-ecological zones: the dry midlands/lowlands (20%), the midlands (48%) and the highlands (32%). In Sidama region mixed agriculture (crop and livestock production) is practiced. Major crops grown include: enset, coffee, maize, wheat, teff, barley, haricot bean and khat. Enset is the main staple crop both in highlands and midlands while maize is so in the lowlands. There are two cropping seasons in Sidama Zone: belg and meher. Belg rains are mainly used for land preparation and planting of long cycle crops such as maize and sorghum and seed bed preparation for meher crops. The meher rains are used for planting of cereal crops like barley, teff, wheat and vegetable crops. Besides, meher rains are also responsible for the growth and development of perennial crops such as enset,

coffee and khat. Food security is more precarious in the lowland areas of Aleta Wondo, Borecha, Darra, Bensa, Loka Abaya and Hawassa Zuria woredas mainly due to moisture stress and water logging in some pocket areas hampering agricultural production, less diversification of food sources and minimum use of improved farm inputs due to lack of cash and credit facilities to purchase the inputs. The Sidama region administration has a total of 4063 health professional of different disciplines and 524 Health Posts, 127 Health Centers, 1 general and 12 District hospital owned by government and additionally there are 21 private and 3 NGO clinics, 65 private rural drug venders. The overall potential health service coverage of the Zone by public health facilities are 90.3%.

Study design

a prospective cohort study design will be conducted from March 1 2022 to November 30 2022

Source population

All pregnant women attending ANC clinic at public hospitals of Sidama region.

Study population

Pregnant women selected by using simple random sampling technique from the prior three months ANC register of selected public hospitals and meet inclusion criteria

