Eligibility criteria

Inclusion Criteria

Attend ANC in the last 3 months

Permanent residence with possible contact

Plan to deliver in the region

Exclusion Criteria

Severe anemia / sever illness

Sample size determination

Sample size calculation for the second objective

The sample size for Exposed and Non-Exposed is calculated using Epi Info version 7 soft-ware by taking a proportion of low birth weight among non anemic women of 14.6%, AOR of 3.17, study power of 80%, an Exposed to Non-Exposed ratio of 1:1 and a non-response rate of 15%. Finally a total of 180 (90 Anemic mothers and 90 non-anemic mothers) sample size was calculated.

Table 1: Sample size calculation

| Factors | Ratio of controls to cases | % of outcome in unexposed | AOR | Power | CI | Exposed | Non Exposed | Final sample size | Source |
|---------|----------------------------|---------------------------|------|-------|-----|---------|-------------|-------------------|---------|
| Anemia | 1:1 | 14.6 | 3.17 | 80 | 95% | 78 | 78 | 156 | AZ |
| Anemia | 1:1 | 11.2 | 3.81 | 80 | 95% | 68 | 68 | 136 | Sodo |
| Anemia | 1:1 | 13.02 | 3.51 | 80 | 95% | 70 | 70 | 140 | Kembata |

Sampling techniques

From 18 public hospitals found in the region we randomly selected 6 hospitals. Enumeration of prior three month's ANC register was conducted. Then, based on the number of ANC register, the sample size was proportionally allocated for all selected public hospitals in the region (Figure 1).

Exposed (pregnant women having anemia) and non-exposed (pregnant women not having anemia) will be selected by using simple random sampling technique from the prior three months ANC register of each selected public hospital and followed until delivery to see the incidence of low birth weight.

[figure not shown]

Figure 2: Schematic representation of sampling procedure

Study variables

Dependent variable: Birth Weight

Independent variable

- Socio-demographic factors
- Reproductive related
- Medical related
- Health promotion
- Anemia

Operational definitions

Anemia: any hemoglobin level below 11g/dl in pregnancy is considered as anemia (5,6).

Weight (Kg): will be measured by electronic scales with digital display (UNICEF SECA Electronic weight scale (± 10 precision scale) and Participants will be asked to remove their shoes and any bulky clothing during measurement will be taken.

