Three day intensive training will be given on how to perform standardized height and weight measurement and on interviewing techniques using standard checklist and structured questionnaire. The checklist and questionnaires will be translated into a regional working language (Sidamu Affo). Supervision will be conducted. Double data entry will be done and the questionnaire will be pretested on 5 % of total sample size at Dilla city. The calibrated instrument will be used to measure height and weight.. During data collection, continuous supervision will be done by the supervisors and principal investigator.

Data processing and analysis

The data will be entered into Epidata software and exported to SPSS software for windows version 23. for analysis. Descriptive statistics will be computed and both bivariable and multivariable logistic regression will be employed to identify effect of anemia on birth weight Independent sample student t test will be used to compare the mean difference in birth weight in anemic and non-anemic pregnant women. Multi variable Logistic Regression will be done to establish association of anemia with birth weight.

Ethical consideration

Prior to data collection appropriate ethical clearance and supportive letter will be obtained from the Ethical Review Committee of Hawassa College of Health Science. Written permission will be obtained to undertake the study from the selected hospitals. Participation in the study will be based on voluntary base and the participants

will be informed about the right to withdraw at any time from the study. Confidentiality will be assured by using anonymity. Pregnant women who had anemia (Hb<11g/dl) will be provided with Iron-folate tablets. Written consent will be requested from every study participant included in the study during data collection time after explaining the objectives of the study. For this purpose, a one page consent letter was attached to the cover page of each questionnaire stating about the general objective of the study and issues of confidentiality which was discussed by the data collectors before proceeding with the interview.

Work plan

Table 2 : Showing the work plan of the study in Sidama Region, 2022

| Activity | Oc t | Nov | De c | Jua n | Fe b | Mar | Ap r | May | Ju n | Jul | Au g | Se p | Oc t | No v | De c |

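### The only planned comparison of birth weight in grams is an unadjusted t-test, although the groups are neither randomised nor matched and shared causes are collected

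*Protocol*

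**What the plan says.** The Objective is "To establish association between anemia and birth weight among pregnant women attending ANC clinic at public hospitals of Sidama region", and Study variables gives "Dependent variable: Birth Weight". The Operational definitions also split birth weight at 2,500 g.

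Data processing and analysis assigns two methods:
- For the association: "Multi variable Logistic Regression will be done to establish association of anemia with birth weight". The Summary reports this as an adjusted odds ratio with 95% CI, so it concerns the LBW split. Bivariable logistic regression is planned as well.
- For the mean: "Independent sample student t test will be used to compare the mean difference in birth weight in anemic and non-anemic pregnant women".

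No adjusted analysis of birth weight in grams is stated.

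On design, the protocol says "a prospective cohort study design will be conducted from March 1 2022 to November 30 2022". Under Sampling techniques, exposed and non-exposed women "will be selected by using simple random sampling technique from the prior three months ANC register of each selected public hospital". No matching is mentioned.

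**The concern.** Simple random sampling from a register makes each group representative of its own kind. It does not make anemic women comparable with non-anemic women. If anemic women more often have malaria, live in rural areas, have short birth intervals or are poorer, and these factors lower birth weight in their own right, the raw difference in means includes their effect as well as that of anemia.

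At stake is how the figure in grams is read. The Statement of problem presents the study as a response to a gap in causal evidence. A crude mean difference printed beside an adjusted odds ratio invites readers to treat the two as equally controlled, and they are not.

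**Working it through.** **1. Are there shared causes, and are they collected?** The Statement of problem reports that "the type of residence, gravidity, interval between pregnancies, and malaria infection during pregnancy have been associate with gestational anemia". For poor fetal growth in developing countries, the Literature Review lists "poor gestational nutrition, low pre-pregnancy weight, short maternal stature, and malaria". Side by side:

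| Factor | Tied to anemia in | Tied to birth weight or LBW in | Questionnaire item |
|---|---|---|---|
| Malaria | Statement of problem | Literature Review, LBW risk factors | Yes |
| Rural residence | Statement of problem | Literature Review, LBW risk factors | Yes |
| Birth interval | Statement of problem | Literature Review, LBW risk factors | Yes |
| Wealth or income | Statement of problem | Background, LBW determinants | Yes |

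All four appear on both sides and can be adjusted for with data the study will hold.

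**2. The plan's own figure.** There is no sample size for the t-test; the study is sized on LBW. Inputs from Sample size determination: 14.6% LBW in non-anemic women, odds ratio 3.17, 80% power, 95% confidence.
- LBW in anemic women: odds 0.146/0.854 × 3.17 = 0.542, so 0.542/1.542 = 35.15%.
- Mean proportion 0.2488. Uncorrected n = [1.960·√(2 × 0.2488 × 0.7512) + 0.842·√(0.146 × 0.854 + 0.3515 × 0.6485)]² / 0.2055² = 68.3.
- With continuity correction: (68.3/4) × [1 + √(1 + 4/(68.3 × 0.2055))]² = 77.7, so 78 per group. This matches Table 1.
- 156 × 1.15 = 179.4, so 180. This matches the stated total.

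**3. How large could the confounding be?** For a binary factor worth b grams, with prevalence differing by Δ between the groups, the raw difference shifts by b × Δ. The documents give neither b for these four factors, nor Δ, nor the SD of birth weight. The following are assumptions that show scale only. With 76 women per group (90 less 15%, rounded down), SE = SD × √(2/76). The last three columns give the two-sided type I error of a 5% test when anemia has no effect.

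| Assumed SD | SE | Shift 10 g (100 g × 10 points) | Shift 40 g (200 g × 20 points) | Shift 90 g (300 g × 30 points) |
|---|---|---|---|---|
| 400 g | 65 g | 5% | 9% | 28% |
| 500 g | 81 g | 5% | 8% | 20% |
| 550 g | 89 g | 5% | 7% | 17% |

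One modest, mildly imbalanced factor does little. A strong one, or several clustering in the same women, would matter.

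**4. Does the gram analysis carry information worth adjusting?** Assume birth weight is normal with a common SD and that anemia shifts the whole distribution. The planned LBW rates then imply a shift of z(0.3515) − z(0.146) = −0.381 + 1.054 = 0.672 SD (336 g if the SD is 500 g). Power at 76 per group, crude t-test against an uncorrected two-proportion test:
- odds ratio 3.17: 98.5% against 84.1%
- odds ratio 2.5 (0.528 SD): 89.8% against 62.5%
- odds ratio 2.0 (0.394 SD): 67.5% against 38.7%

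For a given odds ratio these figures do not depend on the SD. They do depend on the normal, common-SD shift, and they describe the crude comparison, not the adjusted model.

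**The case against.** The strongest reply is that the inference already rests on an adjusted model. The protocol gives the task of establishing the association to multivariable logistic regression, sizes the study on LBW and ties no conclusion to the t-test. That stands, and it limits the weight of the point. A second reply is that an extra adjusted model is the kind of detail left to an analysis plan. That holds less well: the protocol is not silent here. It names a method for the mean difference, and that method cannot adjust.

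A reader might infer more than the documents support:
- *That the mean comparison is confounded by design.* Neither design nor analysis controls confounding of this estimate, but its presence and size are unknown.
- *That a conflict between the gram result and the adjusted odds ratio could not be explained.* Crude and adjusted odds ratios will both exist, and their gap indicates the direction and rough strength of measured confounding. It does not supply an adjusted difference in grams.
- *That the 138 g reduction with HIV infection, cited in the Literature Review, measures the bias.* The prevalence of HIV in each group is not given. The questionnaire shown has no HIV item, so the proposed model could not adjust for it either.
- *That the t-test is simply the most powerful analysis.* The protocol does not say so. The advantage depends on the assumed shift and would weaken if anemia acted mainly in the lower tail.

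**Conclusion.** The point holds in limited form. The protocol adjusts the LBW result but fixes an unadjusted test as the only analysis of birth weight in grams. The cohort is unmatched, and the protocol's own text names shared causes that its questionnaire records. The mean difference may therefore be confounded, and the documents do not allow the amount to be computed. The 10 to 90 g range rests on assumed factor effects, prevalence gaps and SDs; it is not an estimate. The defect does not undermine the adjusted odds ratio. It should be corrected because a better method is available on data already planned, and because, under a normal common-SD shift, the gram outcome carries more information than the LBW split.

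**What to change.** Add to Data processing and analysis a multivariable linear regression of birth weight in grams on anemia, reported as an adjusted mean difference with 95% CI. Adjust for a pre-specified set of collected pre-exposure confounders and for hospital, and use the same set in the LBW logistic model. Malaria, residence, birth interval and income are the natural starting list. Label the t-test as a crude, descriptive result. Robust standard errors or a slope per g/dl of hemoglobin are optional and not needed to cure this fault.

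The cost is modest: some extra analysis in the planned software, with no new data or participants. The real work is naming the set, since Study variables lists only broad groups.
- Items that follow the exposure, such as gestational age at birth, do not belong in the set. Malaria needs care because the questionnaire does not record whether it came before the hemoglobin measurement.
- The set must be short. At the planning rates, 76 × (0.146 + 0.3515) gives about 38 LBW births. Anemia, four single-parameter confounders and five indicators for six hospitals make 10 parameters, or about 3.8 LBW births each in the logistic model. The linear model would have 152/10, about 15 weights each.

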The etiology of anemia is multifactorial with nutritional deficiencies (iron and folate), infectious diseases (hookworm, schistosomiasis, malaria and HIV) and genetic red blood cell disorders(sickle cell and thalassaemias) being key contributors[23].

In pregnant women, a favorable iron status is a prerequisite for a good course of pregnancy. There is evidence that iron deficiency, even in the absence of iron deficiency anemia, may have a negative impact in non-pregnant

women, e.g. in terms of decreased cognitive ability and physical performance [25]. In pregnant women it may impair fetal and infant development [24].

Low maternal hemoglobin levels are associated with increased risk of preterm delivery and low birth weight [26,27]. Prenatal prophylactic iron supplementation deserves further examination as a measure to improve birth weight and potentially reduce health care costs [28].

A randomized controlled trial suggested that prophylactic iron supplementation begun in early pregnancy can reduce third trimester anemia and improve birth outcomes [23]. However, a recent study showed that anemia during early pregnancy was not associated with increased risk of adverse perinatal outcomes, and anemia in later pregnancy was inversely associated with preterm birth and low birth weight [29].

The relationship between anemia and birth weight is still not clear. The previous study approaches in Sidama as well as in Ethiopia gave no evidence of a temporal relationship between exposure (anemia) and outcome (low birth weight) There is a gap to entirely infer causality between anemia and LBW.

The purpose of this study protocol is to investigate the association of anemia with birth weight among pregnant women attending ANC Clinic at Public Health Facilities of Sidama Region in the future

Significant of the study

Despite the efforts made by the government and other stakeholders, anemia during pregnancy is still a public health problem in Ethiopia. In Sidama, to the best of current knowledge, no research exists that has used prospective cohort study design to establish the association of anemia with birth weight. The finding of this study would help to guide the antenatal care service providers and other concerned stakeholders in Sidama Region to work more on prevention and control of anemia and low birth weight

Literature Review

Risk factors of Low Birth Weight (LBW)

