|---------------------------------------|---------|-----|---------|----------|---------|-----|---------|-----|---------|-----|---------|---------|---------|---------|---------|
| Research proposal Preparation | | | | | | | | | | | | | | | |
| Final proposal submission and Defense | | | | | | | | | | | | | | | |
| Obtaining ethical Clearance | | | | | | | | | | | | | | | |
| Giving training | | | | | | | | | | | | | | | |
| Data collection and processing | | | | | | | | | | | | | | | |
| Final paper Submission | | | | | | | | | | | | | | | |
| Defense and dissemination of result | | | | | | | | | | | | | | | |

Questionnaire on birth weight

Socio-demographic characteristics of pregnant women public health facilities (N=180).

| Variables | Coding categories | Skip |
|--|---|-------------|
| Age | _____ | |
| Residence | 1. Rural 2. Urban | |
| Marital status | 1. Never married 2. Married 3. Separated/Widowed | |
| Religion | 1. Orthodox 2. Catholic 3. Protestant 4. Muslim 5. (Specify) | |
| Highest Educational level | | |
| Highest Husband Educational level | _____ | |
| Occupation status | 1. Government employee 2. Private employee 3. Merchant 4. House wife 5. (Specify) | |
| Family income | _____ | |
| Family size | _____ | |
| Sex of the newborn | 1. Female 2. Male | |
| Obstetric and baby characteristics of mothers who gave birth at the selected public Hospitals | | |
| Current pregnancy type | 1. Planned 2. Unplanned | |
| Gravidity | | |
| Fertility desire | | |
| Injury history of any source | 1. Yes 2. No | |
| Trimester at 1st visit for the last pregnancy | 1. 1 st 2. 2 nd 3. 3 rd | |
| TT vaccine before or during pregnancy | 1. Yes 2. No | |

| | | |
|---|---|--|
| Iron supplementation for current pregnancy | 1. Yes 2. No | |
| Dietary counseling during the current pregnancy | 1. Yes 2. No | |
| Extra meal during current pregnancy | 1. Yes 2. No | |
| History of abortion | 1. Yes 2. No | |
| History of still birth | 1. Yes 2. No | |
| Obstetric and baby characteristics of mother who gave birth at the selected public Hospitals | | |
| APH during the current pregnancy | 1. Yes 2. No | |
| Substance use during the current pregnancy | 1. Yes 2. No | |
| Alcohol use during the current pregnancy | 1. Yes 2. No | |
| Chronic medical illness | 1. Yes 2. No | |
| Reproductive characteristics of respondents | | |
| Used modern contraceptive | 1. Yes 2. No | |
| Time to book first ANC visit | 1. ≤ 16 weeks 2. > 16 weeks | |

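### Iron-folate is supplied at the same hemoglobin cut-off that defines exposure, so the planned effect of anemia is that of anemia detected and supplied with iron-folate, and one undated iron item cannot separate prior iron from iron given in response

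*Protocol*

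**What the plan says.** - **Exposure.** Under Operational definitions, "any hemoglobin level below 11g/dl in pregnancy is considered as anemia". Women below this level form the exposed group.
- **Provision.** Under Ethical consideration, "Pregnant women who had anemia (Hb<11g/dl) will be provided with Iron-folate tablets". No provision is stated for non-anemic women, and the protocol does not say whether they receive iron through routine ANC.
- **Follow-up.** Under Sampling techniques, both groups are followed to delivery for low birth weight (LBW).
- **Objective and inference.** The Objective is "To establish association between anemia and birth weight among pregnant women attending ANC clinic". Under Data processing and analysis, "logistic regression will be employed to identify effect of anemia on birth weight"; the Summary also speaks of an effect. The Statement of problem describes earlier research in these words: "There is a gap to entirely infer causality between anemia and LBW".
- **Iron and birth outcomes.** The Statement of problem cites one randomized trial as suggesting that "prophylactic iron supplementation begun in early pregnancy can reduce third trimester anemia and improve birth outcomes".
- **Data on iron.** The questionnaire has one Yes/No item, "Iron supplementation for current pregnancy", with no date, source or duration.

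**The concern.** The rule that triggers the tablets is the rule that defines exposure, and the tablets come before the outcome is measured. The anemia whose consequences are observed is therefore anemia that has been found and supplied with iron-folate. The objective, exposure definition, variable list and analysis do not mention this; the provision appears only under ethics.

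Two things follow.

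1. If the supplied iron-folate improves birth weight, the difference between the groups shrinks. A small or null result could then be read as showing that anemia does not matter for LBW, when it may show only that anemia so managed does not. The protocol wants its finding to guide ANC providers, so this misreading would have consequences.
2. The iron item mixes a baseline characteristic (iron taken before the qualifying hemoglobin, possible in either group) with a response to exposure (iron given because hemoglobin was low). If it is asked after provision and entered in the multivariable model, the model adjusts in part for a consequence of exposure.

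**Working it through.** **Step 1. Set the sections side by side.** Exposed means hemoglobin below 11 g/dl (Operational definitions). Supplied with iron-folate means hemoglobin below 11 g/dl (Ethical consideration). The two sets coincide by rule. The outcome comes later, at delivery (Sampling techniques). No regression on these data can therefore recover a contrast between anemia without the tablets and no anemia.

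**Step 2. Reproduce the plan's sample size.** Inputs from Sample size determination and Table 1: LBW in non-anemic women 14.6%, odds ratio 3.17, power 80%, ratio 1:1, 95% confidence (taken as two-sided 5%; sidedness is not stated), non-response 15%.

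- Odds in unexposed: 0.146 / 0.854 = 0.171. Odds in exposed: 0.171 × 3.17 = 0.542. Risk in exposed: 0.542 / 1.542 = 0.3515.
- Two-proportion formula without correction: 69 per group. With the continuity correction: 78 per group, as stated. The same corrected formula gives the stated 68 and 70 for the other two rows.
- Total 156; 156 × 1.15 = 179.4, rounded up to 180, as stated.

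**Step 3. Illustrate a dilution.** The documents give no effect of the supplied tablets on LBW. Let f be the assumed share of the excess risk that they remove. The excess is 0.3515 − 0.146 = 0.2055.

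- Risk in the anemic group: p = 0.146 + 0.2055 × (1 − f)
- Odds ratio: [p / (1 − p)] / 0.171
- Power: normal approximation for two proportions, two-sided 5%, 78 per group, no continuity correction

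| f (assumed) | LBW, anemic | Odds ratio | Power |
|---|---|---|---|
| 0 | 35.1% | 3.17 | 85% |
| 10% | 33.1% | 2.89 | 78% |
| 25% | 30.0% | 2.51 | 64% |
| 50% | 24.9% | 1.94 | 36% |

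The first row shows 85% rather than the planned 80% because the plan's 78 includes the continuity correction. With that correction in the power formula too, the four powers are 80%, 72%, 56% and 29%.

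**Step 4. Check the iron item.** It covers the whole current pregnancy and has two answers. An anemic woman who took iron before her hemoglobin was measured and one who first received it because of that measurement both answer Yes if asked after provision. Nothing else in the questionnaire tells them apart.

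**The case against.** **Iron in the comparison group.** A reader might infer that only anemic women receive iron and that non-anemic women go without. The protocol does not say so. It is silent on their care, and the iron item is put to every woman with no skip by anemia status, so iron use in either group is foreseen. If routine ANC supplies both groups alike, any dilution is smaller. This stands, and it is a reason to record source and timing in both groups.

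**Who supplies the tablets.** The sentence is passive and may describe clinic practice. In that case the cohort reflects anemia as it is managed among ANC attenders, who are the population in the objective. That also stands, but the inference would still concern anemia as managed, and the protocol should say so.

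**Whether iron changes the outcome.** It is tempting to read the protocol as stating that this treatment improves birth outcomes. It reports one trial that suggested early prophylactic iron can do so. That is not tablets given for established anemia at an unspecified gestation, and the protocol describes anemia as multifactorial. Bias toward no association is likely but not certain.

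**Planning odds ratios.** The documents do not say whether the source studies' odds ratios came from treated women. If they did, 3.17 already contains some of the dilution and the table overstates the loss of power.

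**Causal language.** The objective says association, and the remark on causality describes a gap in earlier work. A protocol also has no conclusion to correct. What remains is the wording about an effect of anemia in the Summary and the analysis section.

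**Timing of the iron item.** The protocol does not state when it is asked, so it cannot be said that every supplied woman will be coded Yes. The problem of adjusting for a consequence of exposure is conditional on the item following provision and entering the model.

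**Conclusion.** The point holds as a mismatch between the contrast the study will deliver and the inference it plans, together with a questionnaire item that cannot show the timing of iron. Both follow from the protocol's text: exposure and provision share one cut-off, follow-up runs to delivery, and the iron item is undated.

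The size of any dilution cannot be computed from the documents. Under the assumption that 10% to 50% of the excess risk is removed, the odds ratio falls to between 2.89 and 1.94 and power at 78 per group to between 78% and 36% (uncorrected), and less is lost if the planning odds ratios already reflect treatment. The documents do not support saying that untreated and treated groups are being compared, that non-anemic women receive no iron, or that a bias toward zero is established. The comparison remains usable. The wording of its inference and one questionnaire item should change. The point is no objection to supplying the tablets.

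**What to change.** Leave the provision of iron unchanged.

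1. **Questionnaire, both groups.** Replace the iron item with two: (a) iron taken before the qualifying hemoglobin, Yes/No; (b) iron received after it, with start date and source (study or routine ANC). Use only (a) as a baseline covariate. Report (b) descriptively by group.
2. **Inference.** In the Summary and in Data processing and analysis, replace the wording about an effect of anemia with the association with LBW of anemia detected at ANC and supplied with iron-folate, compared with no anemia. Do not attach a description of care to the non-anemic group, since the protocol gives none. Add that a null result would not show that untreated anemia is harmless.

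The cost is one extra questionnaire line and a narrower claim. The sample size is not affected by this change. Timing and source should be collected during follow-up, because a pooled Yes/No answer may not be separable afterwards.
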